Scientific Research Council of Alanya Alaaddin Keykubat University

**INVESTIGATION OF CANDIDATE miRNAs AS POTENTIAL BIOMARKERS IN
THE THE EARLY DIAGNOSIS OF PROSTATE CANCER AND BENIGN PROSTATE
HYPERPLASIA**

Project number

2020-04-03-MAP01

Project Team

Assoc. [name]. [name] (Correspondence)

Investigators

[name] [name]

[name] [name]

Assoc. [name]. [name]

Assoc. [name]. [name]

The Clinical Research Ethics Committee of the Alanya Alaaddin Keykubat University Faculty
of Medicine

(Ethical Approval No. 10354421-2020/16-24)

(Ethical approval date : 13.02.2020)

Objective and Scope

Prostate cancer (PCa) is one of the most common cancers in men and the second highest cause of cancer-related deaths (Vanacore et al, 2017; Siegel et al., 2019). Early diagnosis of cancer is very important for the clinical evaluation of the patient and selective and effective treatment. Currently, PCa is diagnosed by serum prostate-specific antigen (PSA) measurements, digital rectal examination (DRE) and pathologic evaluation of prostate biopsies performed under transrectal ultrasonography guidance (Bhagirath et al., 2018). PSA value should be measured at least twice for biopsy decision. Although PSA is a guide in the diagnosis of PCa, its level can also be increased in benign conditions such as benign prostatic hyperplasia (BPH) and prostatitis (Abramovic, 2020). Nevertheless, the free/total (f/t) PSA ratio of 4-10 ng/ml is recommended to differentiate between BPH and prostate cancer (Bhagirath et al., 2018; Vanacore et al., 2017; Siegel et al., 2019). However, the PSA level does not provide reliable results and is lower than the determined value in some cancer patients or considerably higher in some BPH patients. This leads to a large number of patients being biopsied unnecessarily or some patients being missed (Abramovic, 2020; Szelisk et al., 2018). More specific, sensitive, and reliable biomarkers are needed in the clinic to aid pre-treatment decision-making, especially to better distinguish malignant from non-malignant conditions, as well as aggressive from non-aggressive tumors (Abramovic, 2020).

MiRNAs are short non-coding RNA sequences of 19-22 nucleotides in length that regulate the expression of various genes post-transcriptionally. MiRNAs can suppress gene expression by targeting several genes, thus acting as tumor suppressors or oncogenes (Cowland et al., 2007; Kanwal et al., 2017). In recent years, miRNAs have been nominated as reliable biomarkers that help us make accurate diagnoses of many diseases such as cancer (Kanwal et al., 2017). Although there are various studies on miRNAs detected in tissues and sera of patients with PCa, there is still very little data on which miRNAs can be used as biomarkers. Moreover, there are conflicting results in the literature regarding various miRNAs, whether they are downregulated or upregulated (Aghdam et al., 2019; Moya et al., 2019; Xu et al., 2015; Zhu et al., 2015).

This study aimed to investigate the roles of miR-134-5p, miR-149-5p, miR370-3p, miR-107, and miR-221 expression levels on the diagnosis and severity of the disease in patients diagnosed with PC and BPH. In addition, it was aimed to compare some clinical features such as serum PSA and Gleason Score with serum miRNA levels and to determine the relationship between them. The study will contribute significantly to the literature by evaluating these miRNAs, which have been shown to play a role in cell proliferation in various types of cancer (Qi et al., 2019; Su et al., 2017; Zhao et al., 2017) and whose role in PC has not yet been fully elucidated, and will shed light on the evaluation of new diagnostic biomarkers.

2. Material Methods

2.1. Study Design and Patients

The study included 20 PCa patients and 17 BPH patients who are clinically and pathologically confirmed, aged between 40-70 years, with serum PSA levels above 4 ng/mL, who presented to the urology clinic between January 2021 and December 2022. Additionally, 20 healthy volunteers who visited the urology outpatient clinic for routine check-ups were included in the study as the control group. Patients who had undergone drug therapy or surgery for prostate cancer had chronic inflammatory or infectious diseases, were hospitalized within the past year for a chronic illness, or had another known malignancy were excluded from the study.

The Clinical Research Ethics Committee of the Alanya Alaaddin Keykubat University Faculty of Medicine granted ethical approval (Approval No. 13.02.2020/16-24), and informed consent was obtained from all participants.

The clinical diagnosis of patients included in the study was conducted at the Urology Outpatient Clinic of Alanya Alaaddin Keykubat University Training and Research Hospital, with pathological assessments performed in the Pathology Laboratory of the same institution. Serum PSA levels were determined using the ELISA method, and miRNA expression analyses were performed using quantitative real time polymerase chain reaction (qRT- PCR) following miRNA isolation from peripheral blood samples.

2.1.1. Study Criteria

Inclusion Criteria:

- For all groups, between 40-70 years of age.
- Prostate cancer group: Patients with positive digital rectal examination (DRE) results, serum PSA level above 4 ng/mL and a confirmed pathological diagnosis of Prostate cancer.
- BPH group: Patients with a PSA level over 4 ng/mL and a negative DRE result who were clinically and pathologically diagnosed with BPH.
- Control: Healthy volunteers who applied to the urology outpatient clinic for routine check-ups and whose PSA value was below 4 ng/ml.

Exclusion Criteria:

- To have undergone drug therapy or surgery for prostate cancer,
- To have chronic inflammatory or infectious diseases,
- Were hospitalized within the past year for a chronic illness,
- To have another known malignancy,
- Being outside the age limit of 40-70.

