2.2. Blood Samples and PSA Levels

Two milliliters of peripheral venous blood were collected from the volunteers included in the study into EDTA tubes. Serum PSA immunoassays evaluated for clinical examinations were determined on the automated immunoassay analyser.

2.3. miRNA Expression with Quantitative Real-Time PCR Reaction (qRT-PCR)

miRNA was extracted from the peripheral blood samples of volunteers using the Hybrid-R™ miRNA Isolation Kit and applied the following steps according to the manufacturer's instructions. Subsequently, according to the manufacturer's instructions, miRNA was converted to cDNA using the miR cDNA Synthesis Kit. A total of 20 μ l volumes of reactions containing miRNA-specific stem-loop primers were performed for each sample.

The expression levels of miR-107, miR-134-5p, miR-149-5p, miR-370-3p, miR-221-5p were measured by quantitative real-time PCR using miRqGreen MasterMix and the reaction was performed according to the manufacturer's instructions. Expression levels of each miRNA were calculated using the comparative cycle threshold (ct) method according to the formula $2^{-\Delta\Delta Ct}$ (Livak & Schmittgen, 2001). The fold change ratio of each miRNA was determined and compared with that of the control.

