2.4. Statistical Analysis Plan (SAP)

All statistical analysis and graphs were performed using GraphPad Prism-5 (version 9.0) and SPSS 21.0 software. The normal distribution of the data was evaluated with the Shapiro-Wilk test. The results were expressed as mean \pm standard deviation ($x\pm SD$) for continuous variables such as age that showed normal distribution and as median (Interquartile range [IQR]) for continuous variables that did not show normal distribution, such as PSA levels. Categorical variables were compared using the chi-square test.

miRNA (miR-107, miR-134-5p, miR-149-5p, miR-370-3p, miR-221-5p) expression levels did not show normal distribution, and statistical analyses were performed using the Kruskal-Wallis or Mann Whitney-U test. The relationship between miRNAs and serum PSA levels and Gleason scores was analyzed using the Spearman correlation test.

The role of miRNAs as biomarkers in prostate cancer was investigated by drawing the receiver operating characteristic (ROC) curves and the area under the ROC curve (AUC), cut-off point, sensitivity and specificity for each miRNA was calculated. Statistical significance was taken as $p < 0.05$.

3. Important Dates

Ethical approval date : 13.02.2020

Study Start and Completion: June 1, 2020- March 2, 2023

Patient registration start and completion: 26.01.2021-05.12.2022

The project duration lasted 2 years and 9 months in total.

The project's final report was presented to the Scientific Research Council of Alanya Alaaddin Keykubat University on 02.03.2023. The final report was accepted at the board meeting dated 08.03.2023.

4. References

Aghdam SG, Ebraze M et all.(2019)The role of microRNAs in prostate cancer migration, invasion, and metastasis. *J Cell Physiol*, 234:9927-9942. <https://doi.org/10.1002/jcp.27948>

Cowland, J. B., Hother, C., & Gronbaek, K. (2007). MicroRNAs and cancer. *APMIS*, 115(10), 1090-1106. doi: 10.1111/j.16000463.2007.apm_775.xml.x.

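### Entry rules make DRE status identical to group in PCa vs BPH, and the 4 ng/mL PSA cut identical to group in PCa vs control, so the ROC claims need a stated comparator and a restricted scope

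*Combined protocol and SAP*

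**What the plan says.** Section 2.1.1 sets these entry rules, with an age range common to all groups:

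- PCa: "Patients with positive digital rectal examination (DRE) results, serum PSA level above 4 ng/mL and a confirmed pathological diagnosis of Prostate cancer".
- BPH: "Patients with a PSA level over 4 ng/mL and a negative DRE result who were clinically and pathologically diagnosed with BPH".
- The third group, serving as controls: "Healthy volunteers who applied to the urology outpatient clinic for routine check-ups and whose PSA value was below 4 ng/ml". No DRE requirement or result is given for controls.

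Section 2.1 gives the numbers: "The study included 20 PCa patients and 17 BPH patients who are clinically and pathologically confirmed, aged between 40-70 years", plus 20 healthy volunteers.

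Section 2.4 states the diagnostic analysis: "The role of miRNAs as biomarkers in prostate cancer was investigated by drawing the receiver operating characteristic (ROC) curves", with an AUC, and "cut-off point, sensitivity and specificity for each miRNA was calculated". It does not name the non-cancer group for the curves, does not bring DRE or PSA into the ROC analysis, and does not say to which men the results apply. A control reference is named only for expression, in section 2.3: "The fold change ratio of each miRNA was determined and compared with that of the control". Section 2.4 also says: "The relationship between miRNAs and serum PSA levels and Gleason scores was analyzed using the Spearman correlation test".

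Objective and Scope lists PSA, DRE and biopsy pathology as today's diagnostic route. It notes that PSA is low in some cancers and high in some BPH, and calls for better markers to tell malignant from non-malignant disease. The title concerns early diagnosis.

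**The concern.** The groups to be told apart are partly defined by the tests that the miRNAs are set against. Pathology fixes the diagnosis, but DRE is then required to agree with it: positive in every cancer, negative in every BPH. In PCa vs BPH, a miRNA that differs because of cancer and one that differs because of whatever makes the DRE positive would give the same data. In PCa vs control, the 4 ng/mL cut plays the same part.

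The rules also remove the men for whom a new marker would matter most on the protocol's own rationale: cancers with low PSA, cancers missed by DRE, and BPH with a positive DRE. Section 2.4 nevertheless plans a cut-off, sensitivity and specificity for each miRNA as a prostate cancer biomarker, without limiting the population. Such figures can be taken to apply to men who could not enter the study.

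**Working it through.** The documents give no accuracy target, power calculation or AUC, so there is no stated figure to reproduce. The core of the check follows from the entry rules.

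**Inputs.** Group sizes are 20 PCa, 17 BPH and 20 controls (section 2.1). DRE and PSA status are those required by section 2.1.1; they are not reported data.

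**1. Tables implied by the rules**

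| | PCa | BPH | Control |
|---|---|---|---|
| DRE positive | 20/20 | 0/17 | not stated |
| PSA above 4 ng/mL | 20/20 | 17/17 | 0/20 |

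For a binary test, AUC = (sensitivity + specificity)/2.

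- DRE, PCa vs BPH: (1 + 1)/2 = 1.00.
- PSA cut, PCa vs control: (1 + 1)/2 = 1.00.
- PSA cut, PCa vs BPH: (1 + 0)/2 = 0.50. The cut does not separate these groups, but the comparison is conditional on PSA above 4 ng/mL.

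The two values of 1.00 result from selection and are not estimates of test accuracy. They leave no room to show an increment over that test in that contrast.

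**2. Pairs that could inform accuracy beyond DRE or the PSA cut**

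- PCa vs BPH: 20 × 17 = 340 pairs. Both DRE-positive: 20 × 0 = 0. Both DRE-negative: 0 × 17 = 0. Total within a stratum: 0 of 340.
- PCa vs control: 20 × 20 = 400 pairs. Both above 4 ng/mL: 20 × 0 = 0. Both below: 0 × 20 = 0. Total: 0 of 400.

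A logistic model of PCa vs BPH on DRE plus one simulated marker cannot be fitted (singular matrix, complete separation). A larger sample under the same rules would not help. The unadjusted AUC, by contrast, uses all 340 or 400 pairs and can be calculated.

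**3. What a marker of DRE status alone would show.** Assume a normally distributed marker shifted by d SD with DRE status and unrelated to cancer within a DRE stratum. Its PCa vs BPH AUC is Φ(d/√2): 0.64, 0.76 and 0.86 for d = 0.5, 1.0 and 1.5. Its within-stratum AUC is 0.50 throughout. The values of d are assumed.

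**4. Range of possible overstatement among men with PSA above 4 ng/mL.** Let s be the share of such cancers that are DRE-positive and q the share of such BPH that are DRE-negative. The documents give neither, and the observed sensitivity (Se) and specificity (Sp) of 0.80 are also assumed.

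- Lower end: the miRNA does not depend on DRE. Both figures stay at 0.80, and the overstatement is zero.
- Worst case: the miRNA follows DRE status only, so DRE-positive BPH behaves like DRE-positive cancer.
  - Sensitivity over all such cancers = Se·s + (1 − Sp)(1 − s). At s = 0.3, 0.5, 0.7: 0.24 + 0.14 = 0.38; 0.40 + 0.10 = 0.50; 0.56 + 0.06 = 0.62.
  - Specificity over all such BPH = Sp·q + (1 − Se)(1 − q). At q = 0.6, 0.75, 0.9: 0.48 + 0.08 = 0.56; 0.60 + 0.05 = 0.65; 0.72 + 0.02 = 0.74.

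The enrolled data cannot say where between these ends the truth lies. Cancers with PSA of 4 ng/mL or below are outside even this range.

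**The case against.** The strongest reply is that no planned calculation fails. Section 2.4 plans no analysis adjusted for, or incremental to, DRE or PSA. The title speaks of candidate and potential biomarkers, the aim is framed around men already diagnosed, and a case-control comparison of 57 men is a usual first step. The BPH arm, with PSA above 4 ng/mL, does address the benign disease with raised PSA that Objective and Scope describes. The final report has been accepted and is not among the documents, so it may already limit its inference.

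Much of this stands, and it rules out several stronger readings that a reader might infer:

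- *The ROC analysis is invalid or cannot be run.* Not supported: the unadjusted AUCs are calculable and describe the men sampled.
- *Sensitivity is really 0.38 to 0.62, or specificity 0.56 to 0.74.* Not supported: these are worst cases on inputs that the documents do not give.
- *DRE also confounds PCa vs control.* Not supported: control DRE status is not stated.
- *The study has no early-stage cancers.* Not supported: no criterion selects or identifies them, but none excludes them.
- *The DRE condition is undisclosed because the text of 2.1 omits it.* Not supported: subsection 2.1.1 states it for both groups.
- *DRE confounds the Gleason correlation.* Not supported: it is an analysis within cancer cases, where DRE is constant by rule. Those cases are still all DRE-positive with PSA above 4 ng/mL, so the limit on scope applies to it too.

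What the reply does not meet is the gap between the rationale and the sample. Objective and Scope sets the markers against PSA and DRE and cites low-PSA cancers. The plan then reports sensitivity and specificity with no comparator and no population. An exploratory aim does not supply either.

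**Conclusion.** The point holds as one about identifiability and scope. By rule, DRE status is the group label in PCa vs BPH, and the 4 ng/mL cut is the group label in PCa vs control. That part assumes only that the entry rules were followed. The ROC results therefore cannot distinguish a cancer marker from a marker of DRE status in PCa vs BPH. They cannot show value beyond DRE in that contrast or beyond the PSA cut against controls, and they give no evidence for DRE-negative cancer, low-PSA cancer or DRE-positive BPH.

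The results may overstate accuracy in those men. The size is unknown: it runs from none, if the miRNA does not depend on DRE, to the worst case shown above, which rests on assumed s, q, sensitivity and specificity. As written, the plan does not support an unrestricted early-diagnosis objective. Correcting this changes what may be concluded, not what is calculated for each contrast.

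**What to change.** For the enrolled set (registration closed on 05.12.2022):

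1. In section 2.4, specify separate ROC curves for PCa vs BPH and for PCa vs control, each with its own AUC, cut-off, sensitivity and specificity.
2. Restrict the objective and the inference to separating DRE-positive, PSA >4 ng/mL cancer from DRE-negative, PSA >4 ng/mL BPH and, separately, from controls with PSA <4 ng/mL.
3. State that added value over DRE (PCa vs BPH) or over the PSA cut (PCa vs control) was not assessed and cannot be recovered by adjustment. State also that DRE-negative cancer, low-PSA cancer and DRE-positive BPH were not sampled.
4. Qualify the early-diagnosis wording accordingly.
5. Attach the same limit to the Gleason correlation: it applies to DRE-positive, PSA >4 ng/mL cancers.

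Repeating the DRE rule in the text of 2.1 is not needed.

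The cost is wording in the objective, section 2.4 and the interpretation, with no new data or laboratory work. The downside is a narrower and less favourable conclusion.

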2.2. Blood Samples and PSA Levels

Two milliliters of peripheral venous blood were collected from the volunteers included in the study into EDTA tubes. Serum PSA immunoassays evaluated for clinical examinations were determined on the automated immunoassay analyser.

2.3. miRNA Expression with Quantitative Real-Time PCR Reaction (qRT-PCR)

miRNA was extracted from the peripheral blood samples of volunteers using the Hybrid-R™ miRNA Isolation Kit and applied the following steps according to the manufacturer's instructions. Subsequently, according to the manufacturer's instructions, miRNA was converted to cDNA using the miR cDNA Synthesis Kit. A total of 20 μ l volumes of reactions containing miRNA-specific stem-loop primers were performed for each sample.

The expression levels of miR-107, miR-134-5p, miR-149-5p, miR-370-3p, miR-221-5p were measured by quantitative real-time PCR using miRqGreen MasterMix and the reaction was performed according to the manufacturer's instructions. Expression levels of each miRNA were calculated using the comparative cycle threshold (ct) method according to the formula $2^{-\Delta\Delta Ct}$ (Livak & Schmittgen, 2001). The fold change ratio of each miRNA was determined and compared with that of the control.

2.4. Statistical Analysis Plan (SAP)

All statistical analysis and graphs were performed using GraphPad Prism-5 (version 9.0) and SPSS 21.0 software. The normal distribution of the data was evaluated with the Shapiro-Wilk test. The results were expressed as mean \pm standard deviation ($x\pm SD$) for continuous variables such as age that showed normal distribution and as median (Interquartile range [IQR]) for continuous variables that did not show normal distribution, such as PSA levels. Categorical variables were compared using the chi-square test.

miRNA (miR-107, miR-134-5p, miR-149-5p, miR-370-3p, miR-221-5p) expression levels did not show normal distribution, and statistical analyses were performed using the Kruskal-Wallis or Mann Whitney-U test. The relationship between miRNAs and serum PSA levels and Gleason scores was analyzed using the Spearman correlation test.

The role of miRNAs as biomarkers in prostate cancer was investigated by drawing the receiver operating characteristic (ROC) curves and the area under the ROC curve (AUC), cut-off point, sensitivity and specificity for each miRNA was calculated. Statistical significance was taken as $p < 0.05$.

3. Important Dates

Ethical approval date : 13.02.2020

Study Start and Completion: June 1, 2020- March 2, 2023

Patient registration start and completion: 26.01.2021-05.12.2022

The project duration lasted 2 years and 9 months in total.

The project's final report was presented to the Scientific Research Council of Alanya Alaaddin Keykubat University on 02.03.2023. The final report was accepted at the board meeting dated 08.03.2023.

4. References

Aghdam SG, Ebraze M et all.(2019)The role of microRNAs in prostate cancer migration, invasion, and metastasis. *J Cell Physiol*, 234:9927-9942. <https://doi.org/10.1002/jcp.27948>

Cowland, J. B., Hother, C., & Gronbaek, K. (2007). MicroRNAs and cancer. *APMIS*, 115(10), 1090-1106. doi: 10.1111/j.16000463.2007.apm_775.xml.x.

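### Age is neither matched nor adjusted for, so an age difference between the groups could be read as a miRNA difference

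*Combined protocol and SAP*

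**What the plan says.** Section 2.1 describes three non-randomised groups. The patients are 20 with PCa and 17 with BPH. For comparison, "20 healthy volunteers who visited the urology outpatient clinic for routine check-ups were included in the study as the control group".

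Section 2.1.1 sets one age rule, "For all groups, between 40-70 years of age", and repeats it as an exclusion criterion. Beyond that, controls are defined by health, check-up attendance and a PSA below 4 ng/ml. Nothing ties their ages to those of the patients.

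In section 2.4 age appears once, as an example of how variables are summarised: mean and SD are used "for continuous variables such as age that showed normal distribution". The miRNA "expression levels did not show normal distribution, and statistical analyses were performed using the Kruskal-Wallis or Mann Whitney-U test". Spearman correlation is planned with PSA and Gleason score, but not with age. For the ROC analysis, the "cut-off point, sensitivity and specificity for each miRNA was calculated". No regression, stratification, covariate-adjusted ROC or age sensitivity analysis is mentioned, and no test of age between groups is named.

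**The concern.** In a non-randomised comparison, a variable that differs between the groups and also relates to the marker will produce a marker difference by itself. Age is an obvious candidate here. It is recorded, and a 30-year window leaves room for the groups to differ by several years. The planned rank tests and ROC curves would carry such a difference straight into the p-values, AUCs, cut-offs, sensitivities and specificities.

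The stated aim is diagnostic, so an age-driven separation would be reported as biomarker performance. Both conditions are needed: an age gap between the two groups compared, and an age-miRNA association. If either is absent, no harm follows. PCa versus BPH is affected only if those two groups themselves differ in age.

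**Working it through.** The plan states no effect size, power or group ages, so there is no figure of its own to reproduce. The check asks how far an age gap alone would move the planned test and AUC.

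**Inputs from the documents.** Group sizes 20 PCa, 17 BPH, 20 controls and ages 40-70 (section 2.1); significance at p < 0.05 (section 2.4), taken as two-sided.

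**Assumptions, not in the documents.** Age-miRNA correlation r of 0.2-0.4; mean age gap of 3, 5 or 8 years; ages normal but truncated to 40-70, giving a within-group SD of about 6.4-6.8 years. The gaps are then d = 0.44, 0.75 and 1.25 SD. No disease effect.

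**Step 1, AUC from age alone.** The miRNA shift in SD units is r × d, so AUC = Φ(r·d/√2).
- Central case, r = 0.3, d = 0.75: Φ(0.225/1.414) = Φ(0.159) = 0.563
- Mild end, r = 0.2, d = 0.44: Φ(0.088/1.414) = 0.525
- Far end, r = 0.4, d = 1.25: Φ(0.5/1.414) = 0.638

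**Step 2, false-positive rate, PCa versus control.** The null standard error of the AUC is √[(20+20+1)/(12×20×20)] = √(41/4800) = 0.092. With z = (AUC − 0.5)/SE, the rejection rate is about Φ(−1.96+z) + Φ(−1.96−z).
- Central: z = 0.68, rate 0.105
- Mild end: z = 0.27, rate 0.058
- Far end: z = 1.50, rate 0.321

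**Step 3, simulation.** The normal approximation was checked against 10,000 simulated studies per cell. Each cell gives the Mann-Whitney rejection rate for PCa versus control, with the mean AUC in brackets.

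| r | 3 years | 5 years | 8 years |
|---|---|---|---|
| 0.2 | 0.058 (0.525) | 0.069 (0.542) | 0.116 (0.571) |
| 0.3 | 0.065 (0.537) | 0.093 (0.564) | 0.200 (0.606) |
| 0.4 | 0.089 (0.552) | 0.145 (0.585) | 0.322 (0.639) |

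With zero gap the rate is 0.048-0.053, and with zero correlation 0.045-0.051. The three-group Kruskal-Wallis test gives 0.055-0.313.

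**Step 4, PCa versus BPH (20 v 17).** With equal ages the rate is 0.045-0.053. If these two groups differ by 3-8 years it is 0.056-0.304.

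**Step 5, with age in the model.** A linear model on group and age holds the PCa-versus-control rate at 0.047-0.053 in every cell, and a rank ANCOVA at 0.048-0.053. Under heavy-tailed or skewed noise and a quadratic age effect, the linear model stays at 0.041-0.056.

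**Step 6, precision cost when age is irrelevant.** In the three-group model the PCa-control variance factor goes from 1/20 + 1/20 = 0.1 to 0.1 + d²/54, where 54 = 57 − 3. The standard error ratio is √(1 + d²/5.4), which is 1.02, 1.05 and 1.14 at 3, 5 and 8 years. Simulation gives the same values, and 1.22 at 10 years.

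**Step 7, whether an age test would settle it.** With 20 v 20 and an assumed SD of 6-7 years, power to detect an age gap is 27-35% for 3 years and 62-75% for 5 years. A non-significant age comparison would therefore not rule out a gap that matters.

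**The case against.** The case for leaving the plan alone is reasonable on several points.

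- **Neither condition is evidenced.** The documents show no age gap and no age-miRNA association, so 6%-32% describes the assumed grid and not this study. This stands. A separate run with a correlation of 0.5 and a gap of about 7.8 years reached 0.507, which shows how far the top end depends on what is assumed.
- **The central effect is modest.** An AUC shift of 0.064 is about 0.7 standard errors (0.064/0.092), and even 0.639 lies inside the null sampling range of 0.5 ± 1.96 × 0.092, about 0.32-0.68. Five uncorrected independent tests at 0.05 give a larger familywise rate, 1 − 0.95⁵ = 23%. Both statements are true. They bear on priority, and leave the age bias in place.
- **Group ages are results.** One would not expect them in a methods text, and summarising age is already planned. That is fair, but a summary does not adjust the tests or the AUC, and the by-group comparison is not stated.
- **Restriction to 40-70 is a genuine design control.** It is, and it makes the far end less likely. A gap of several years still fits inside it.
- **PCa versus BPH is the more relevant contrast.** There the rate is about 5% unless those groups differ in age. This limit is accepted. The ROC comparator is not named, so the AUC figures above assume controls.
- **The support for adjustment is circular**, because the data were generated with a linear age effect. The runs with non-normal noise and a quadratic age effect answer this for the test. The age-adjusted AUC was not simulated, and it will be imprecise with 17-20 per group.
- **Age is not the only difference.** PSA and DRE differ by design, and age adjustment leaves that untouched.

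**Conclusion.** The concern holds. No age matching is described, and none of the planned group tests or ROC curves can take age into account, so any age gap stays inside the reported p-values, AUCs and cut-offs.

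Whether this happened cannot be told from the documents. In the central assumed case (correlation 0.3, gap 5 years, PCa versus control) the false-positive rate is about 9% instead of 5%, with an AUC of 0.56 from age alone. Over the assumed grid the rate is 6%-32% and the AUC 0.53-0.64. It is about 5% if either condition is absent. These figures are illustrations and not estimates for this study. The change is worth making because it is inexpensive and would show whether the problem applies. Confidence in its practical importance is medium.

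**What to change.** 1. Report age by group, with the differences between groups and not only a p-value.
2. For each miRNA, fit a linear model of log2 fold change (that is, −ΔΔCt, already available from the section 2.3 calculation) on group and age. Use a rank ANCOVA if the residuals are clearly non-normal.
3. Give age-adjusted contrasts with 95% confidence intervals for PCa versus control and PCa versus BPH.
4. Give an age-adjusted AUC beside the unadjusted one, naming the method and the comparator group.
5. Keep the planned rank tests and ROC curves alongside.
6. If the age ranges overlap poorly, say so and describe the adjusted result as dependent on the linear age term.

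The cost is a supplementary analysis of data already held; the final report was accepted on 08.03.2023, and no new samples are needed. Adjustment uses one degree of freedom among 57 participants. If age turns out to be unrelated to the miRNA, the PCa-control standard error grows by about 2% at a 3-year gap, 14% at 8 years and 22% at 10 years. With 17-20 per group, adjustment should stay with age or very few covariates.

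### Section 2.4 does not say who enters the miRNA-PSA Spearman test, how diagnosis group is handled, or which non-case group each ROC curve uses

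*Combined protocol and SAP*

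**What the plan says.** **Aim.** Under Objective and Scope, the study examines the miRNAs "on the diagnosis and severity of the disease in patients diagnosed with PC and BPH". A separate sentence adds that "it was aimed to compare some clinical features such as serum PSA and Gleason Score with serum miRNA levels". That second sentence names no population.

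**Groups.** Section 2.1 gives 20 PCa patients, 17 BPH patients and 20 controls. Section 2.1.1 defines them partly by PSA:
- PCa: "Patients with positive digital rectal examination (DRE) results", with "serum PSA level above 4 ng/mL and a confirmed pathological diagnosis of Prostate cancer".
- BPH: "Patients with a PSA level over 4 ng/mL and a negative DRE result who were clinically and pathologically diagnosed with BPH".
- Controls: "Healthy volunteers who applied to the urology outpatient clinic for routine check-ups and whose PSA value was below 4 ng/ml".

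**Analysis.** Section 2.4 has one sentence on correlation: "The relationship between miRNAs and serum PSA levels and Gleason scores was analyzed using the Spearman correlation test". It has one on ROC analysis of the miRNAs as prostate cancer biomarkers, from which "the area under the ROC curve (AUC), cut-off point, sensitivity and specificity for each miRNA was calculated". The first gives neither an analysis set nor any treatment of group. The second implies PCa as the case group and leaves the non-cases open. Section 2.3 names the control as the reference for fold change, but not for the ROC curves. No other section fills either gap, and nothing suggests that text was removed here.

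**The concern.** Because eligibility fixes every control below every patient on PSA, a Spearman test over all 57 participants partly measures whether someone is a patient. Any miRNA that differs between patients and controls will then tend to correlate with PSA, even if the two are unrelated within each group. Restricting to the 37 patients removes the effect of the 4 ng/mL cut, but not a PCa-BPH difference in both PSA and the miRNA. The miRNA-PSA relationship is a stated aim, so a reader needs to know whether a reported rho describes a relationship within a diagnosis or a difference between diagnoses.

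For the ROC curves, the AUC, cut-off, sensitivity and specificity cannot be interpreted without the comparator. Objective and Scope states the need as separating malignant from non-malignant disease and notes that PSA is also raised in BPH. PCa versus BPH addresses that need directly. PCa versus healthy controls is a different question, also within the design.

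**Working it through.** The plan gives no correlation, AUC, power or sample-size figure, so there is nothing of its own to reproduce. All miRNA shifts and PSA distributions below are assumptions.

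**Inputs from the documents.** n = 20 PCa, 17 BPH, 20 controls (Section 2.1). PSA above 4 ng/mL in both patient groups and below 4 in controls (Section 2.1.1). Threshold p<0.05 (Section 2.4), taken as two-sided.

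**Step 1: expected pooled rho with no within-group association.** Take a miRNA shifted by d SD in both patient groups. The probability that a patient exceeds a control is A = Φ(d/√2). With N = 57, 37 patients and 20 controls, the mean-rank difference is N(A − 0.5) for the miRNA and N × 0.5 for PSA, where separation is complete. The rank variance is (N² − 1)/12. Hence

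rho ≈ 6 × 20 × 37 × (A − 0.5)/(57² − 1) = 4440(A − 0.5)/3248.

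- d = 0.5: A = 0.638, rho ≈ 4440 × 0.138/3248 = 0.19.
- d = 1.0: A = 0.760, rho ≈ 4440 × 0.260/3248 = 0.36.

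The critical value is t/√(df + t²), which is 0.26 at 55 df. A 1 SD shift therefore puts the expected rho above the threshold.

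**Step 2: share of studies with p<0.05.** Simulation, 20,000 studies per scenario. PSA is lognormal with log-SD 0.6 or 0.8, truncated at 4. The median parameter is 1.2 for controls, and 10/8 or 20/7 for PCa/BPH. The miRNA is normal and independent of PSA within each group.

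| Assumed miRNA shift | All 57 | PCa + BPH (37) | Stratified by group (37) |
|---|---|---|---|
| None | 5% | 5% | 5% |
| 0.5 SD, PCa and BPH | 29% | 5% | 5% |
| 1.0 SD, PCa and BPH | 80% | 5% | 5% |
| 1.0 SD, PCa only | 35-68% | 6-42% | 5% |

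The ranges in the last row come from the assumed PSA medians and spread. A separate simulation with other PSA assumptions gave about 5% to 30% for the 37 patients in that row: about 5% when PSA is alike in PCa and BPH, and more when PSA is also higher in PCa. PCa alone (n = 20) stays at about 5% throughout. A three-group stratified test (n = 57, 53 df) also holds about 5%.

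**Step 3: AUC by comparator.** The binormal AUC is Φ(difference/√2). Against both non-case groups it is the 20:17 weighted mean. PCa is raised by an assumed 1 SD.

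| BPH shift | vs controls | vs BPH | vs both |
|---|---|---|---|
| 1 SD | 0.76 | 0.50 | (20 × 0.760 + 17 × 0.500)/37 = 0.64 |
| 0.5 SD | 0.76 | 0.64 | (20 × 0.760 + 17 × 0.638)/37 = 0.70 |
| 0 | 0.76 | 0.76 | 0.76 |

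**Step 4: precision.** The Hanley-McNeil variance is [A(1 − A) + (n₁ − 1)(Q₁ − A²) + (n₂ − 1)(Q₂ − A²)]/(n₁n₂), with Q₁ = A/(2 − A) and Q₂ = 2A²/(1 + A). For 20 versus 17 at A = 0.7: (0.210 + 19 × 0.0485 + 16 × 0.0865)/340 = 0.0074, SE 0.086, half-width 1.96 × 0.086 = 0.17. At A = 0.6 and 0.8 the half-widths are 0.18 and 0.14.

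**The case against.** The strongest reply is that the text is silent, not wrong. One sentence covers both PSA and Gleason score. Gleason score belongs to the PCa group, so a PCa-only PSA test is a natural reading, and it carries no group confounding. Section 2.4 does not call the test unstratified; that would be inferred from silence. This stands, and it limits the point to an ambiguity under which some readings are confounded and others are not.

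A second reply is that the aim does not ask for a within-diagnosis relationship. An association across groups is real, and reporting it with its set named would be defensible. That also stands. The percentages in Step 2 are therefore rates of detecting an association explained by group, not false-positive rates. The error would lie in reading such a result as a link between miRNA and PSA apart from diagnosis.

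Third, the comparator makes no difference to the AUC if BPH and controls have the same miRNA distribution. This is true, as the last row of Step 3 shows, but the plan does not assume it.

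Fourth, the accepted final report may name the sets and comparators. It is not among the documents, so this cannot be ruled out.

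A reader might infer that controls were in fact pooled. The documents do not say so. The wording about patients with PC and BPH belongs to the diagnosis-and-severity sentence, and it only weakly suggests a patients-only set for the PSA correlation.

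**Conclusion.** The point holds as a gap with consequences. Section 2.4 leaves open the correlation set, the handling of group and the ROC comparator, while Section 2.1.1 ties PSA rank to group. Followed as a plain Spearman test over combined groups, the plan gives a group-confounded answer to a stated aim: about 29% to 80% significant results for shifts of 0.5 to 1.0 SD in both patient groups (n = 57), and about 6% to 42% for a 1 SD shift in PCa only (n = 37). The AUC of one marker can run from 0.50 to 0.76 by comparator. These sizes rest on assumed shifts and PSA distributions; they show direction and range, not trial results.

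It does not follow that every permitted analysis is confounded, that any reported correlation is spurious, or that any reported AUC is inflated. The Gleason correlation is not affected. The change should be made, but it does not by itself invalidate the study.

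**What to change.** In Section 2.4:

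1. Test each miRNA against PSA with a Spearman correlation stratified by diagnosis group (partial Spearman with group as covariate). State which groups enter and show the within-group rho alongside. State that the Gleason correlation uses PCa only. Keeping or excluding controls is a choice to be declared, since the stratified test holds its level either way.
2. Name the comparator for every ROC curve. Report PCa versus BPH separately from PCa versus controls. Any curve against BPH plus controls is additional and labelled as such.

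Optionally, show PSA descriptively on the PCa-versus-BPH curve only. Against controls its AUC is 1.0 by eligibility and carries no information.

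**Cost.** New SAP wording and re-analysis of data already collected.
- Over the 37 patients the stratified test (34 df) needs |rho| of at least 2.032/√(34 + 2.032²) = 0.33, against 0.26 for a pooled test of 57. Its power is about 39%, 63% and 85% for an assumed within-group correlation of 0.3, 0.4 and 0.5. Including controls as a third stratum raises the power at 0.4 to about 80%, if the relationship is similar in them.
- The test assumes a similar relationship across groups, which is why the within-group values should be shown.
- PCa-versus-BPH AUC intervals will be wide, with half-widths of about 0.14 to 0.18.
- Section 3 records acceptance of the final report on 08.03.2023, so any re-analysis must be labelled post hoc.
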